Rationale. Our preliminary data in mice suggest that RE enhances adipocyte catecholamine sensitivity through a novel mechanism involving the delivery of muscle-specific miR-1 to adipose via exosomes. The in vitro analyses in Aim 1 will explore this process mechanistically, with Aim 2 extending the analyses to primary human myotubes and adipocytes. The purpose of this aim is to determine if our working model translates to humans *in vivo*. Analyses of serum exosomes, muscle and adipose tissue isolated before and after a bout of RE will determine if miR-1 potentially mediates muscle-adipose crosstalk during exercise in humans. The ability of isolated exosomes to induce adipocyte lipolysis *in vitro* by enhancing catecholamine sensitivity through CEBP α activation of β AR-3 expression will be assessed.

Design. Relatively sedentary, generally healthy lean (BMI <25) and obese (BMI >30) men and women between 18-30 years of age without study contraindications will be recruited (see inclusion/exclusion criteria in Human Subjects section). Potential eligibility will be assessed by self-reported height and weight, and by reporting no participation in regular (>1 day per week) exercise for at least the past three months. All potential participants will arrive fasted to the Center for Clinical and Translational Sciences (CCTS). After giving written, informed consent, a detailed medical history form will be filled out to screen for eligibility. Measures of physical activity level will be collected before baseline blood, adipose, and muscle samples are taken. We intend to recruit an equal number of lean and obese participants (n=40 in each group, 20 men and 20 women). Power analysis based on the change we observed in miR-1 abundance in exosomes following a bout of knee extensions in a pilot study of 10 individuals, indicated that n=36 is required in each group. We are requesting n=40 in both the lean and obese groups based on an expected difference in means between 1 and 1.95 and an expected standard deviation of 0.45, with the power set at 0.8 and alpha at 0.05. This will accommodate 10% drop out prior to completing all biopsies.

Following a brief rest period, subjects will perform two lower body RE tasks to failure (knee extension and leg press) with blood samples drawn pre- and immediately, 30, 60 and 90 minutes post-exercise. Biopsies of the vastus lateralis and abdominal subcutaneous adipose tissue will be obtained pre- and post-exercise (at approximately 60 and 90 min post, respectively; see graphic abstract in the Human Subjects section).

Experiment 3.1. Exosomal, muscle, and adipose miR-1 abundance will be quantified, as well as miR-1A/B primary transcripts in muscle and adipose by qPCR as described in the SOP section.

Experiment 3.2. Isolated exosomes from the 30 and 60 minute time points will be applied to differentiated ADHASC for 24 hr, and lipolysis *in vitro* and the β AR-3 pathway gene expression assessed as described in the SOP section. Pre-RE exosomes will be transfected with miR-1 mimic (Pre-plus) and 30 minute post-RE exosomes with anti-miR-1 oligonucleotide (Post-minus) and compared to mock transfected exosomes from those time points. These modified exosomes will be incubated with differentiated adipocytes to parallel Aim 1 mouse Experiments 1.1 and 1.2.

Methods.

Resistance exercise (RE). Following determination of each subject's one repetition max (1-RM, see Human Subjects section for detailed description), subjects will perform two exercises, knee extension and leg press at 80% of 1-RM, designed to work the quadriceps. Subjects will perform three sets of eight repetitions, with a 90-120 second rest between sets, with a fourth set performed to failure. RE will be performed on pneumatic resistance devices (Keiser Sports Health Equipment, Fresno, CA).

Muscle biopsy. A muscle biopsy will be obtained from the vastus lateralis at baseline and approximately 1 hr post-exercise under local anesthetic (1% Xylocaine HCl, 3cc). A 1/4 inch wide incision will be made and a sterile 5mm Berkstrom biopsy needle (Pelomi Industries, Denmark) inserted with suction to obtain a 100-200 mg muscle sample. [name], study physician and co-investigator on this project, has extensive experience with this procedure. It is well-tolerated and volunteers routinely provide multiple samples^{83,89,94-96}. Muscle is snap frozen in liquid nitrogen and stored at -80°C until RNA isolation.

Adipose Biopsy. An abdominal subcutaneous fat biopsy sample will be obtained from the lower abdominal wall prior to and approximately 90 min post exercise. The adipose biopsy procedure is similar to the thigh muscle biopsy procedure, except that 1-2 g of adipose tissue is routinely obtained^{42,79,94,97,98}.

Human serum analyses. Glucose and insulin will be measured in the University of Kentucky CCTS Biochemical Analysis Laboratory^{99,100} from baseline serum collected from fasting lean and obese participants

to calculate HOMA-IR (Glucose*Insulin/405) as a measure of muscle insulin sensitivity. NEFA and free glycerol will be measured ⁸¹ both at baseline and in serum collected at multiple time points following the resistance exercise bout, and used to calculate a simplified “anti-lipolytic index” (NEFA*Insulin), which indicates adipocyte insulin sensitivity based on insulin’s ability to suppress lipolysis ¹⁰¹. In humans, fasting serum norepinephrine is positively associated with isoproterenol ED₅₀ in isolated adipocytes. Thus, elevated fasting catecholamines may be indicative of decreased adipose tissue catecholamine sensitivity ¹⁰². We will also measure serum epinephrine and norepinephrine by HPLC (Vanderbilt University Hormone & Analytical Services Core) ¹⁰³.

Statistical Analysis. The College of Health Sciences supports the effort of a biostatistician through the Office of Research to provide dedicated support to funded investigators. A one-way repeated measures ANCOVA adjusting by sex will be used to determine if a significant difference exists between the groups in response to RE for miR-1 and miR-1A/B primary transcripts. If a significant difference is detected, LSD *post-hoc* comparisons will be performed to identify the source of significance with $p \leq .05$. The Pearson correlation coefficient will be used to determine whether muscle, serum, and adipose miR-1 and miR-1A/B primary transcripts are correlated to tissue insulin sensitivity and fasting catecholamines at baseline. All statistical analyses will be performed using SAS[®] 9.4 (SAS institute, Cary NC).

Expected outcomes and alternative approaches. We expect that the bout of lower extremity RE will result in decreased miR-1 abundance in muscle at 60 minutes, a rapid and transient increase in exosomal miR-1, and a subsequent increase in adipose miR-1 abundance at 90 minutes. We do not anticipate changes in miR-1 primary transcript abundance in adipose tissue which would support our hypothesis that miR-1 is delivered via exosomes. miR-1 is highly expressed in muscle and we acknowledge that a single bout of RE may not significantly decrease muscle miR-1 expression, even if it is packaged and released in exosomes. Moreover, 60 minutes post-exercise may not be the appropriate time point to detect this change. Our pilot time course blood sampling study following RE suggested that miR-1 in serum exosomes is highest at 30 minutes and is beginning to decrease by 1 hr post exercise. Thus, we expect delivery to adipose should be detectable at 90 minutes. We acknowledge that this time point may not enable us to capture any changes in downstream targets of miR-1, but will provide proof-of-principle for a large scale clinical exercise trial that would include additional post-exercise time points following an acute bout of RE, as well as a training component.

We expect that lean individuals will be more insulin sensitive than obese individuals, and that obese participants will display higher fasting NEFA in the context of higher fasting insulin (due to decreased adipose tissue insulin sensitivity). Including both lean and obese individuals will determine if adiposity affects the miR-1 acute response to RE. It is possible that release of miR-1 in exosomes from muscle will be lost or blunted in the obese cohort. However, we hypothesize that insulin sensitivity (assessed by HOMA-IR and the anti-lipolytic index) will be positively correlated to the serum miR-1 excursion following the RE bout in both populations. NEFA and glycerol will be measured both pre- and post-RE to determine whether changes in NEFA and glycerol from baseline are correlated with change in miR-1 in serum and/or adipose from baseline. We will also determine if the induction of adipocyte lipolysis *in vitro* is different in exosomes isolated from lean compared to obese participants following RE. Further, the *in vitro* studies will provide the opportunity to explore additional aspects of adipocyte metabolism that may be regulated by miRs, which will be informed by results of Aims 1 and 2. Overall, we expect results from this study to inform the design of a resistance exercise training trial in obese individuals. Moreover, the proposed studies are expected to provide the fundamental knowledge necessary to determine if exosomal miR-1 delivery to adipose tissue has the potential to form the basis for the development of a novel therapeutic strategy to treat obesity, particularly in individuals physically unable to exercise.

Table 1 provides our projected timeline for the proposed experiments. As discussed above, the preliminary data presented demonstrate that we have the necessary expertise to perform the proposed experiments so we do not anticipate any major delays; however, the experiments have been laid out to accommodate unforeseen delays such that the proposed experiments and analyses will be completed by the end of Year 5.

Table 1. Timetable for proposed experiments.

Specific Aim	Year 1	Year 2	Year 3	Year 4	Year 5
Aim 1: Determine if exercise-induced exosomal miR-1 enhances adipocyte adrenergic signaling through activation of β 3-AR expression.	breed, mature mice to 4 mo., perform Exp 1.1 analyze data	perform Exp 1.3 analyze data	breed, mature mice to 4 mo., perform Exp 1.4 analyze data	write manuscript	
Aim 2: Determine if skeletal muscle fiber-derived exosomes promote adipocyte lipolysis through enhanced β -adrenergic signaling.		perform Exp 2.1 analyze data	perform Exp 2.3 analyze data	write manuscript	revise manuscript & additional exp.
Aim 3: Determine if an acute bout of resistance exercise in humans promotes miR-1 mediated adipocyte lipolysis.	recruit & test subjects (n=27)	recruit & test subjects (n=27)	recruit & test subjects (n=26)	perform Exp. 3.1 analyze data	write manuscript
				perform Exp. 3.2 analyze data	revise manuscript & additional exp.

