The primary role of adipose tissue is to store excess energy as lipids, and it is the principal source of serum non-esterified fatty acids (NEFA) during times of energy demand (i.e., fasting or exercise). As such, the metabolic function of adipose is critical for determining whole body metabolic outcomes. Adipocyte lipolysis is driven by catecholamines (norepinephrine and epinephrine), which stimulate β -adrenergic receptors (β -AR; β -1, β -2, and β -3). β -AR agonism enhances insulin sensitivity, lean mass, energy expenditure, and thermogenesis ²⁹⁻³³. A growing body of work indicates that adipocytes develop catecholamine resistance in the context of obesity and insulin resistance ³⁴⁻⁴¹, potentially due to down-regulation of β -AR ³⁵. We and others have shown that adipose miRNAs are altered with obesity and insulin resistance ⁴²⁻⁴⁴. Moreover, miRNAs in adipose have been shown to modulate β -AR signaling in vivo ⁴⁵ and in vitro ⁴⁶. These data, along with our preliminary data, indicate that miRNA-mediated mRNA processing can improve adipose β -AR sensitivity, leading to the exciting hypothesis that exosomal delivery of miRNAs to adipose could be used to ameliorate metabolic disease.

Numerous studies in humans and animals have shown that aerobic exercise is beneficial to adipose tissue function and whole-body metabolism ^{10,11,47-49}. Both acute and chronic aerobic exercise enhance adipocyte catecholamine sensitivity in humans and animals ⁵⁰⁻⁵⁶. Although relatively few studies have investigated whether adipose adrenergic signaling is affected by RE, it is known that a single bout of RE can increase circulating NEFA and resting energy expenditure and decrease respiratory quotient for up to 24 hours ⁵⁷⁻⁶¹, indicative of increased adipocyte lipolysis and muscle fatty acid oxidation. Furthermore, the lipolytic response to RE is impaired in obese men ^{62,63}. Using synergist ablation, a model of RE in mice, we show that adipose transcriptional responses are exosome-dependent, and that serum exosomes enhance adipocyte catecholamine sensitivity and lipolysis for at least 24 hours (Fig. 6). To our knowledge, this is the first demonstration of a potential mechanism whereby RE imparts metabolic adaptations in adipose. Since adipose metabolic function is crucial for determining whole-body metabolic outcomes, the ability of RE-induced exosomes to improve adipose metabolism has significant clinical implications.

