In an effort to identify how miR-1 might be affecting gene expression in adipose tissue, we performed a microarray analysis on adipose collected from vehicle or GW4869 treated mice after one day of either sham surgery or synergist ablation. Our initial search strategy was to identify genes whose expression was changed in response to RE in the vehicle group but were unchanged in the GW4869 group (relative to their respective sham). Using this strategy, we identified the up-regulation of genes involved in adrenergic signaling (β 3-AR and C/EBP α) and lipolysis (HSL, ATGL, TGL, PLIN1 and FABP2) in adipose of vehicle-treated mice following RE; however, following GW4869 treatment, the expression of these same genes was either unchanged or down-regulated (Fig. 5A). To insure the up-regulation of lipolytic genes in adipose was not caused by a decrease in food intake, we measured food intake and body weight throughout the experimental period. As shown in Fig. 5B-C, food intake and body weight remained unchanged and, in particular, for the Vehicle-RE group. These microarray results suggest that lipolysis was activated following RE through β -adrenergic signaling and prevented when exosome release was blocked by GW4869 treatment.

To determine if RE in fact enhances catecholamine sensitivity of adipose tissue, we measured the ability of adipocytes isolated from mice subjected to either sham surgery (Control) or synergist ablation (RE) to release non-esterified fatty acids (NEFA) in response to 100 μ M isoproterenol. As shown in Fig. 6, RE adipocytes released significantly more NEFA into the media than did Control adipocytes in response to

[figure not shown]
isoproterenol. These findings are consistent with the increase in the expression of β 3-AR and lipolytic genes presented in Fig. 5.

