Experiment 1.2. To determine if miR-1 is necessary and sufficient to enhance adipocyte catecholamine sensitivity, Control exosomes will be transfected with miR-1 mimic (Control-plus) and RE exosomes with anti-miR-1 oligonucleotide (RE-minus). These modified exosomes will be incubated with 3T3-L1 adipocytes for 24 hr and then gene expression and catecholamine sensitivity measured as described in the SOP section.

Experiment 1.3. Based on our preliminary data, we hypothesize that RE-induced exosomal miR-1 is repressing expression of AP-2 α , a negative regulator of C/EBP α . To determine if AP-2 α is a target gene of miR-1 we will generate a luciferase reporter gene harboring the 3'-UTR of AP-2 α . We will assess the ability of miR-1 to

repress reporter gene expression; if so, then we will repeat the experiment with a mutant AP-2 α 3'-UTR reporter gene in which the predicted miR-1 binding site is mutated as previously described by us²⁴.

Experiment 1.4. Microarray analysis of epididymal adipose showed increased expression of genes involved in β -adrenergic signaling and lipolysis in response to RE that was blocked by GW4869 treatment (see Fig. 5). The purpose of this experiment is to use qPCR to confirm the microarray results and, importantly, determine if the observed changes in gene expression and effects of GW4869 treatment are the same in female mice (n=12/sex).

Statistical Analysis. A two-factor ANOVA (treatment X sex) will be used to determine if a significant interaction exists between factors for each dependent variable under consideration. If a significant interaction is detected, Scheffé post-hoc comparisons will be performed to identify the source of significance with $p \leq .05$.

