Expected Outcomes & Alternative Approaches. The preliminary data presented demonstrate that we have the necessary expertise to carry out the proposed experiments so we do not anticipate any technical issues. We expect to confirm the change in β -adrenergic signaling and lipolytic gene expression and the enhanced catecholamine sensitivity of adipocytes exposed to RE-induced exosomes. Moreover, we expect to confirm the basis for these exosome-mediated effects is the exosomal delivery of miR-1 to adipocytes. In particular, we expect to find that Control exosomes containing the miR-1 mimic will promote the same up-regulation in gene expression and enhanced catecholamine sensitivity as do RE exosomes. By contrast, we anticipate the introduction of an anti-miR-1 into RE exosomes will prevent the changes in gene expression and catecholamine sensitivity. What is more difficult to predict is whether or not AP-2 α is a bona fide target gene of miR-1. The miR-1 binding site within the 3'-UTR of the AP-2 α transcript does not conform to a "classical" miRNA binding site but the predicted thermodynamics of miR-1 binding of $\sim\Delta G = -20$ is relatively favorable so there is a reasonable chance we will see miR-1 regulation of AP-2 α expression.

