Experiment 2.1. The purpose of this experiment is to confirm our preliminary results showing the down-regulation of miR-1 in myotubes in response to electrical stimulation and if there is a corresponding increase in muscle-specific exosomal miR-1 abundance. If this relationship is confirmed, we will next treat myotubes with GW4869 to block exosome release to determine if the down-regulation of myotube miR-1 expression with electrical stimulation is mediated by the exosomal export of miR-1 as shown in vivo (see Fig. 4). The expression/abundance of miR-1 will be determined by qPCR as described in the SOP section.

Experiment 2.2. Exosomes from non-stimulated and stimulated myotubes will be incubated with primary human adipocytes for 24 hr and then gene expression and catecholamine sensitivity measured as described in the SOP section. Adult-derived human adipocyte stem cells (ADHASC) were isolated previously from lipo-aspirates⁹¹. [name] lab has expanded and frozen ADHASC from 6 different individuals available for these experiments. We will begin with one line which has been already shown to differentiate very reproducibly and determine the effect of exosomes derived from stimulated and non-stimulated myotubes on gene expression and catecholamine sensitivity as described in the SOP section.

Experiment 2.3. The purpose of this experiment will be to determine if muscle-specific exosomal miR-1 is necessary and sufficient to enhance adipocyte catecholamine sensitivity. Non-stimulated exosomes will be transfected with miR-1 mimic (Control-plus) while stimulated exosomes will be transfected with anti-miR-1 oligonucleotide (Stim-minus). These modified exosomes will then be incubated with primary human adipocytes for 24 hr and gene expression and catecholamine sensitivity measured as described in the SOP section.

Statistical Analysis. A two-factor ANOVA (treatment X sex) will be used to determine if a significant interaction exists between factors for each dependent variable under consideration. If a significant interaction is detected, Scheffé post-hoc comparisons will be performed to identify the source of significance with $p \leq .05$.

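### Aims 1 and 2 draw conclusions about GW4869 blocking without a planned test of whether GW4869 changes the response; if unchanged is read as non-significant, a partial effect will usually pass as a block

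*Combined protocol and SAP*

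**What the plan says.** The Preliminary Data section describes a microarray of adipose tissue from vehicle- and GW4869-treated mice after sham surgery or synergist ablation (RE). The search was for genes that met two conditions, each judged against the matching sham group: "identify genes whose expression was changed in response to RE in the vehicle group but were unchanged in the GW4869 group". For the adrenergic and lipolytic genes found this way, "following GW4869 treatment, the expression of these same genes was either unchanged or down-regulated". The section concludes that the results suggest lipolysis was activated by RE and "prevented when exosome release was blocked by GW4869 treatment". Elsewhere the wording is firmer. The background states that "we show that adipose transcriptional responses are exosome-dependent", and the text on AP-2α and CKIP-1 calls the block complete.

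Two planned experiments build on this. In Experiment 1.4, "The purpose of this experiment is to use qPCR to confirm the microarray results" and to see whether the GW4869 effects are the same in females, with n=12/sex. Experiment 2.1, if its first step succeeds, adds GW4869 to myotubes to "determine if the down-regulation of myotube miR-1 expression with electrical stimulation is mediated by the exosomal export of miR-1 as shown in vivo".

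The Statistical Analysis paragraphs of Aims 1 and 2 are identical: a two-factor ANOVA, treatment by sex, with Scheffé comparisons at p ≤ .05 if the interaction is significant. For the miR-1 inhibitor in Experiment 1.2, Aim 1 states: "we anticipate the introduction of an anti-miR-1 into RE exosomes will prevent the changes in gene expression and catecholamine sensitivity".

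**The concern.** Exosome dependence means that the RE response under vehicle differs from the RE response under GW4869. Comparing two verdicts, changed in one arm and unchanged in the other, does not test that difference. The second verdict is a claim of no effect. If it rests on a non-significant result, it also occurs when a real response remains but the sample is too small to detect it.

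The planned model does not fill the gap. A treatment by sex interaction asks whether the sexes differ. If it is not significant, the plan names no follow-up comparison involving GW4869. If it is significant, the plan does not say which Scheffé comparison decides the GW4869 question.

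At stake is whether the Aim 1 and Aim 2 reports can separate a response that GW4869 abolishes from one that it only reduces. The anti-miR-1 expectation is open to the same problem if necessity is inferred from RE-minus not differing significantly from Control.

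**Working it through.** **The plan's own figure.** The n=12/sex comes from an Aim 1 power calculation for sham versus RE. The effect size, SD and power are not in the available text, so it cannot be reproduced. For reference, 80% power in a two-sided 5% two-sample t-test needs an effect of 1.20 SD at 12 per cell or 1.80 SD at 6 per cell. No error rate or power is stated for the GW4869 comparison.

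**Assumptions.** Normal data, equal SDs, two-sided 5%, unadjusted tests, no sex difference. A cell is one sex by surgery by drug group (8 cells, pooled SD on 8(n−1) df). The plan does not say how n=12/sex is divided, so n is taken as 12 or 6 per cell. The vehicle effect d is assumed to be 1 or 1.5 SD. Unchanged is read as p > 0.05.

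**Formulas.**
- RE versus sham within one sex and drug arm: noncentrality = effect / √(2/n).
- Contrast (RE − sham, vehicle) minus (RE − sham, GW4869): noncentrality = difference / √(4/m), with m mice per surgery-by-drug group.

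**Halved response, d = 1.5 (0.75 SD remains).**
- n=12: 0.75/√(2/12) = 1.84, so it is missed 55.7% of the time.
- n=6: 0.75/√(2/6) = 1.30, so it is missed 75.5% of the time.

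The two tests share a pooled SD, so the rates given a significant vehicle result were simulated:

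| Vehicle effect | True GW4869 effect | 12 per cell | 6 per cell |
|---|---|---|---|
| 1.5 SD | halves response | 56% | 75% |
| 1.5 SD | none | 5% | 27% |
| 1 SD | none | 32% | 59% |

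The entries are the share of significant vehicle results that would be called blocked.

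**In terms of power.** If the vehicle test has 80% power, a halved response is called blocked in 71% of vehicle hits and an unaffected response in 20%. For independent tests with vehicle power P, the joint chance that an inert drug yields a blocked call is P(1−P): 16% at 80% power, and never above 25%.

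**Averaging over sex** (24 per surgery-by-drug group) helps. A remaining 0.75 SD gives 0.75/√(2/24) = 2.60 and is missed about 27% of the time. A remaining 0.5 SD gives 1.73 and is missed about 60%.

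**The direct contrast, averaged over sex.** It rejects 5% of the time when the drug is inert.
- Complete block of 1.5 SD: 1.5/√(4/24) = 3.67, power 95%; 1.5/√(4/12) = 2.60, power about 73%.
- Half block (difference 0.75 SD): 0.75/√(4/24) = 1.84, power about 44%; 0.75/√(4/12) = 1.30, power about 25%.

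**Experiment 2.1.** Ten lines, paired t-test, using the 9% preliminary fall in myotube miR-1 (n=2). The SD of the change is not given and is assumed. If the whole fall persisted under GW4869, it would be missed 28%, 60%, 75% or 86% of the time for an SD of 10, 15, 20 or 30 points. GW4869 is used only after the fall is confirmed. Treating the two steps as independent, the joint chances are 72% × 28% = 20%, 40% × 60% = 24%, 25% × 75% = 19% and 14% × 86% = 12%.

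**The case against.** The strongest reply is that the two-verdict comparison is not a decision rule of the plan. The text introduces it with "Our initial search strategy was to identify genes", in completed preliminary work. It does not equate unchanged with p > 0.05, and its conclusion is hedged. Experiment 1.4 does not adopt it explicitly, and Experiment 2.1 states no criterion. Some genes were down-regulated under GW4869, which is more than a non-significant result, and the figures that might show the tests are missing from the available text. All of this stands, so the non-significance reading is an inference. It does not supply the missing test: no other criterion is stated for what Experiment 1.4 would confirm. Treatment could be a four-level factor that allows the right contrast, but the plan does not say so.

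A reader might infer that a drug with no effect on the response is often reported as a block. The figures do not support that in general: at 1.5 SD and 12 per cell it is 5% of vehicle hits, and it becomes common only when power is low.

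A reader might also infer that the Scheffé correction makes a blocked call more likely. It does not follow. Scheffé is reached only after a significant treatment by sex interaction, and it also suppresses the vehicle result that the pattern requires. With 6 per cell, d = 1 and an inert drug, the joint rate falls from 23% to 2%.

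Finally, the mechanism does not rest on GW4869 alone. Exosomes are applied directly in Experiments 1.1 and 2.2, miR-1 is manipulated in 1.2 and 2.3, and a mutant reporter is used in 1.3. Aim 3 uses no GW4869. This limits the consequence but does not remove it for the GW4869 claims.

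**Conclusion.** The point holds in a limited form. The plan names no test of whether GW4869 changes the response, while parts of the document already describe the response as exosome-dependent or completely blocked. The main risk is that a partial effect is read as a full one: about 56% or 75% of vehicle hits for a halved 1.5-SD response at 12 or 6 per cell. These figures depend on the assumed effect sizes, normal data, unadjusted within-sex tests, the reading of n=12/sex, and unchanged meaning non-significant. Larger effects or averaging over sex reduce them. They are rates for one endpoint and do not give the chance that all the listed genes fit the pattern together. The documents do not show that the existing microarray conclusion is wrong, or that non-significance has been adopted as proof. The plan should be amended on this point; the human study is unaffected.

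**What to change.** In the Aim 1 Statistical Analysis, state that the GW4869 conclusion in Experiment 1.4 rests on (RE − sham, vehicle) minus (RE − sham, GW4869), averaged over sex, and state how n=12/sex is divided among the groups. In Aim 2, use (stimulated − unstimulated, vehicle) minus the same difference under GW4869, computed within line. The treatment by sex term can stay for the sex question.

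Report the response remaining under GW4869 with its 95% CI. Do not write prevented or completely blocked on the strength of a non-significant result under GW4869. A fixed margin for a complete block is not proposed: with a limit of one quarter of the vehicle response, a true complete block of 1.5 SD would qualify only about 25% of the time at 24 per group. For anti-miR-1, rest necessity on RE versus RE-minus directly.

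This costs SAP wording and one contrast per endpoint from planned data, with no extra animals or lines. The price is power. The contrast has twice the variance of a single RE-versus-sham comparison (4/n against 2/n), so 80% power for a complete block needs about 2 times the per-cell n that gives 80% for the simple comparison, and about 2 × 4 = 8 times for a half block. At the planned sizes some claims will become reduced or not shown.
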